In anticipation of a dropout rate of 33% following admission to the hospital (i.e., participants either not ever meeting pain criteria or choosing not to participate), we decided on a sample size of 30 participants with a plan to complete study procedures among the first 20 participants meeting full eligibility criteria. We based our sample size of 20 and definition of feasibility on prior research examining the feasibility of biological sample collection with music therapy (Holochwost et al, 2020). We have no prior experience using the HemaSpot HF for sample collection nor with delivery of the MARI intervention to this population and plan to start with a small sample size in order to refine procedures for a larger study. We hypothesize a 75% feasibility threshold for complete live MARI intervention delivery, PRO collection, and biological sample collection. We would consider failure to be completing less than 15/20 MARI interventions, 15/20 complete sets of PROs at Time 0, Time 1, and Time 2, 80% of MDPRO measures over the duration of the participant's hospitalization, and 45/60 blood sample collections.

We will use descriptive statistics (e.g., counts, percentages, mean, standard deviation, and median) to summarize participants' demographics and clinical characteristics (obtained from EHR), as well as feasibility measures including rates of enrollment, attrition, intervention participation, MARI recording use, biological sample collection/viability, and PRO collection. We will determine the feasibility of biological sample viability by quantifying whether individual participants provided enough biological samples for eventual testing. No formal hypothesis tests (e.g., linear mixed effects models) will be conducted on changes in PRO data as this is a feasibility study.

Blood sample analysis plan

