We are not collecting genetic data. We are not performing any genetic profiling. We are performing gene expression analysis, and this is different from genetic profiling. This is a pilot study to collect information in preparation for an appropriately powered study. To establish procedural elements, it is necessary to test procedures including the MARI intervention, peripheral blood sampling, and mobile device patient-reported outcome collection as these have not been utilized in prior studies with this population. We have already consulted with statisticians and based on our previous findings in music intervention, we need 87 pre- and post-measures on subjects for the fully powered study. After this pilot study, we intend to launch a multi-center feasibility study in collaboration with other institutions.

We will plan on conducting the following gene expression analyses as specified for all three-time points (Time 0, Time 1, and Time 2). The gene expression analysis will be performed at [name] Systems biomedicine lab at Emory University.

A large part of the human genome is transcribed into various forms of RNA, and the global gene expression profile (GEP) changes measure expression changes in genes over time due to an intervention.

Accordingly, our long-term goal of this line of research will be to examine whether pain intensity changes after the MARI intervention are associated with specific changes in gene expression profiles (GEP) and pathophysiologic pathways that correspond with the elicitation of the relaxation response ([name] et al., 2013, 2018; Dusek et al., 2008).

V4 03.22.2024 Page 11 of 16

| HRP- 503BIO | TEMPLATE: UH Biomedical Protocol | | |
|----------------|----------------------------------|----------------|---------|
| Approved: | 09/2021 | Prior Version: | 08/2019 |

Our prior work was conducted among healthy adults ([name] et al., 2013; Dusek et al., 2008) or hypertensive patients ([name] et al., 2018) living in the community using PaxGene tubes to collect whole blood. In the intervening years, the technology of dried blood spot (DBS) collection of samples has improved and has been used for GEP analysis.

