Thus, for the current feasibility study with 30 pancreatic surgical patients with acute post-operative pain, we are primarily interested in understanding the feasibility of collecting the HemaSpot samples from this population and whether the samples collected will be of sufficient quality to allow for gene expression profile testing. The HemaSpot sample will be sent to [name] lab at Emory University for RNA sequencing based transcriptome profiling. The transcriptome profiling will be performed using pairedend RNA sequencing that allows for the measurement of the expression profile of ~30,000 human genes with high sensitivity and specificity. Briefly, sequencing libraries of Poly A selected mRNA will be generated from the double-stranded cDNA using the Illumina TruSeq kit according to the manufacturer's protocol. High-quality libraries will be sequenced on an Illumina Novaseq 6000 to achieve comprehensive coverage of measuring the expression of all genes. The assay can only measure the expression of genes but cannot reveal the identity/race/gender of the subjects.

The Raw sequencing data will be processed to remove any adaptor, PCR primers, and low-quality transcripts. After alignment, the gene expression levels will be normalized and compared among the baseline and post-intervention samples to identify genes that are significantly modulated by the intervention. The comparison will be performed by implementing linear data modeling algorithms comparing the mean and variance among the groups. We will perform a focused analysis on immune and inflammatory response-related genes as our previous analyses depicted that mind-body interventions deliver beneficial effects by affecting these pathways. Additionally, to understand the detailed mechanism of intervention, we will perform pathways enrichment and interactive network analysis.

Although the size of the feasibility proposal is small, we contend that it is worth conducting the GEP for each of the 30 participants across the 3-time points. However, with the small sample it will be beyond the scope of our study to confidently compare the GEP from T0 to T1 to T2. That type of analysis would be conducted in a future randomized trial with a comparison group.

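### The gene-expression plan tests for genes changed by the intervention in a single-arm trial, then puts the comparison out of scope without withdrawing it, and sets no error-rate rule for about 30,000 genes

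*Combined protocol and SAP*

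**What the plan says.** Study Design describes one arm and no randomization. Under Study Procedures, each participant gives a finger-prick sample before the music-assisted relaxation and imagery (MARI) session (T0), directly after it (T1), and 15 minutes later (T2).

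The Blood sample analysis plan commits to gene-expression analyses at all three times. It uses RNA sequencing that "allows for the measurement of the expression profile of ~30,000 human genes". Expression levels will be normalized and "compared among the baseline and post-intervention samples to identify genes that are significantly modulated by the intervention". The method is linear modelling of the mean and variance of groups, followed by a focused look at immune and inflammatory genes. The plan adds: "to understand the detailed mechanism of intervention, we will perform pathways enrichment and interactive network analysis".

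The next paragraph takes a different line: "with the small sample it will be beyond the scope of our study to confidently compare the GEP from T0 to T1 to T2". It continues: "That type of analysis would be conducted in a future randomized trial with a comparison group". The same section gives its priority: "we are primarily interested in understanding the feasibility of collecting the HemaSpot samples from this population", along with whether the samples are good enough for profiling.

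The Data Analysis Plan states: "No formal hypothesis tests (e.g., linear mixed effects models) will be conducted on changes in PRO data as this is a feasibility study". No such statement covers gene expression. No significance level, false discovery rate or other multiplicity rule is given for genes, pathways, the focused gene set or time points.

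**The concern.** One paragraph asks for a list of genes that the intervention has altered and for its mechanism. Both are causal claims, and the design has no comparison group to support them. The paragraph after it says the comparison cannot be made with confidence here, but does not remove it, relabel it as exploratory or change the causal wording. An analyst cannot tell which paragraph to follow.

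If the first is followed, genes and pathways that changed for other reasons, or by chance, could be reported as effects of MARI. The plan describes this pilot as preparation for a larger study, so such a list could steer that study's hypotheses. The length of the list would also depend on a threshold that nobody has fixed in advance.

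**Working it through.** **1. The plan's own figures.** Enrolment follows from 20 completers and 33% dropout: 20 / (1 − 0.33) = 29.85, rounded up to 30. This matches the plan, but it is a dropout allowance, not a basis for gene testing. The 87 pre- and post-measures quoted for a fully powered study come without inputs and cannot be reproduced. The gene analysis has no stated error rate to reproduce.

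**2. The two paragraphs side by side.**

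| Question | Paragraph on the comparison | Paragraph after it |
|---|---|---|
| Is T0 compared with later samples? | Yes, with significance and a mechanism | Not with confidence; left to a controlled randomized trial |
| Reason for a limit | None given | Small sample (explicit); need for a control (implied by the deferral) |
| Are the tests withdrawn or called exploratory? | No | No |

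The bar on formal tests in the Data Analysis Plan is confined to patient-reported outcomes. It covers three 0–10 scales and does not reach the genes.

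**3. Attribution.** For any gene, the expected change from T0 is (effect of MARI) + (change that would have occurred anyway, such as post-operative course or analgesia). A single arm estimates only the sum. The sample size n enters only the standard error, SD of change / √n. Moving from 20 to 87 pairs would multiply the standard error by √(20/87) = 0.48 and leave the second term untouched.

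The Background gives examples of change without music. One cited study reports 19 of 45 markers reversed with music making (42%) and 6 of 45 in a resting control (13%). Another reports 12 pathways changed against 2 in a quiet-reading control. These were different populations and activities. They show that such change occurs, not how much to expect here.

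**4. Small sample is a real but separate limit.** Assumptions: two-sided paired t-test, 80% power, noncentral t distribution, change in units of its within-person SD.

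| n | Detectable change at 0.05 | At 0.05 / 30,000 = 1.67 × 10⁻⁶ (Bonferroni) |
|---|---|---|
| 20 | 0.66 SD | 1.78 SD |
| 30 | 0.53 SD | 1.28 SD |

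The plan is right that the sample is small for this purpose. That explains imprecision, not the lack of attribution.

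**5. Error rate.** Expected chance findings per contrast = genes tested × alpha, if tests are unadjusted and every gene is null. The 30,000 is the plan's figure; every alpha and the filtered gene counts are assumptions.

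| Genes tested | 0.05 | 0.01 | 0.001 |
|---|---|---|---|
| 30,000 | 1,500 | 300 | 30 |
| 20,000 | 1,000 | 200 | 20 |
| 10,000 | 500 | 100 | 10 |

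The plan does not name its contrasts. Two contrasts against T0 would double a cell (2 × 1,500 = 3,000). Correlation between genes does not change the expected count.

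**6. Pairing.** With equal variance σ² at each time and within-person correlation ρ, the mean change has variance 2σ²(1 − ρ)/n. Treating the times as separate groups uses 2σ²/n, which is too large when ρ > 0. The documents do not give ρ. The word for groups may simply mean sets of samples by time, but pairing or blocking by participant is not mentioned.

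**The case against.** The strongest defence is that the section means to sequence now and compare later. The Data Analysis Plan speaks of samples for eventual testing. The Objectives contain no gene-expression effect, and the section puts sample feasibility and quality first. The window is also short: from the start of T0 to the start of T2 it is about 5 + 30 + 5 + 15 = 55 minutes plus the debriefing, which leaves less room for post-operative drift. Analgesic drug, dose and time are recorded.

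Much of this stands, and it rules out several stronger readings that a reader might infer:

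- *That sample size is the plan's only ground for the limit.* It is the only explicit reason, but the following sentence sends the comparison to a trial with a control.
- *That the plan has settled on reporting MARI effects.* The text is unreconciled; it does not establish that intention.
- *That the plan will test without adjustment and produce 1,500 false findings.* It is silent on adjustment, and the counts rest on assumed conditions.
- *That "global gene expression profile (GEP) changes measure expression changes in genes over time due to an intervention" is a causal claim about this trial.* It describes expression profiling in general, and the link to MARI is then called a long-term goal.
- *That using a different finger each time confounds the result.* Nothing in the documents supports this.

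The defence fails on one matter. Comparing later would require the comparison paragraph to be removed or qualified, and it still stands as a set of commitments. A short window and recorded analgesia narrow the alternative explanations but do not replace a comparison group, and the gene analysis names no use of the medication data.

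**Conclusion.** The point holds as a contradiction that should be fixed. The plan specifies significance testing and mechanism analysis with wording that credits the intervention, then places a confident comparison out of scope while leaving both in place. The attribution problem is qualitative: no sample size or p-value rule removes it in a single arm, and it rests on the stated design rather than on any assumed figure.

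The missing error-rate rule and the absence of any mention of pairing are secondary. On its own, the missing rule would be missing detail. The chance-finding counts are illustrative and should not drive the weight given to the point.

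The harm is confined to the gene-expression output. The feasibility criteria in the Data Analysis Plan do not use it, so it would be wrong to infer that the feasibility conclusions are compromised.

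**What to change.** Reconcile the two paragraphs of the Blood sample analysis plan in one of two ways.

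- **Limit the output.** Report RNA quality, sample viability and descriptive within-person variability only, and remove the comparison, pathway and network analyses from this study. This fits the section's stated primary interest.
- **Keep the analyses as explicitly exploratory.** Describe results as *change from T0*, and pathway results as those over-represented among genes that changed from T0. State that no change is attributed to MARI because there is no comparison group, as well as because the sample is small. Name the contrasts, use a paired or participant-blocked model, and control the false discovery rate at a stated level (Benjamini-Hochberg is one option).

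Either choice needs wording only, plus one error-rate rule in the second case. No new data, samples or visits are required. The downside is fewer and weaker gene-level claims from the pilot.

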then the RA will ask the participant if it is ok for the research team to return at another time to see if they meet study criteria and are willing and able to participate in study procedures. If the participant says yes, the RA will return at least 24 hours later and repeat the above steps. If applicable, the RA will return each day that the patient is admitted and study staff are available to repeat the above steps until either (1) the participant's eligibility is confirmed and study procedures begin, (2) the participant says that they are no longer interested in participating in the study at all, (3) the participant becomes ineligible for any other reason (e.g. they are admitted to the ICU, or (4) the participant is discharged. Participants who change their mind about participating (reason 2), become ineligible for another reason (3), or are discharged will be withdrawn from the study. They may still receive music therapy services during their hospitalization after this withdrawal, but these will occur within routine clinical music therapy practice and no data on those sessions will be collected for this study.

The result of both the check in(s) with the provider and with the participant will be documented in REDCap. Participants that continue to meet eligibility criteria on day 1 post-surgery or another day through discharge, and are not withdrawn from the study for the reasons noted above will be considered to have "Initiated study procedures" following enrollment.

V4 03.22.2024 Page 5 of 16

| HRP- 503BIO | TEMPLATE: UH Biomedical Protocol | | | | | |
|----------------|----------------------------------|----------------|---------|--|--|--|
| Approved: | 09/2021 | Prior Version: | 08/2019 | | | |

Sharing of Results with Research Participants

☑ Results will **not** be shared with research participants

☑ Results will **not** be shared with research participants' doctors

Study Design

We will conduct a single arm non-randomized trial to determine the feasibility and acceptability of: (1) a tailored music-assisted relaxation and imagery intervention; (2) biological sample collection; and (3) mobile device patient-reported outcome (MDPRO) collection among adults hospitalized for pancreatic surgery experiencing acute pain. See Attachment "MUSICPUPS_Schematic" for a graphic representation of the study design.

Study Procedures

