Following Time 0, the MT-BC will deliver a standardized 30-minute MARI intervention, personalized to the participant's music and imagery preferences. Prior to the intervention, the MT-BC will verify the participant's music and imagery preferences discussed with the RA during the consent visit. During the MARI intervention, the MT-BC will provide live guitar accompaniment personalized to the participant's music preferences and read from a standardized script directing the participant to relax muscles of the body, practice deep breaths, and explore a relaxing place. This intervention will be recorded live. Following the MARI intervention, the MT-BC will briefly process the participant's experience by asking them how the experience was for them and to describe in their own words how they are feeling after the MARI intervention (please see the attachment "MUSIC PUPS Post MARI Debriefing" for more details). The recorded MARI track will be exported to a Box folder that the participant can access via an app on a study iOS device (e.g., iPod touch, iPhone), or via a web link that is saved as a shortcut on the home screen of the participant's own device. In either case, the participant's MARI use will be tracked in Box.

Immediately following the MARI intervention and post-intervention processing, the MT-BC will leave the participant's room. The RA will then enter the participant's room again. The RA will confirm that the participant is not in too much pain to continue and would like to continue with study procedures, documenting this in REDCap, before collecting post-intervention PROs and peripheral blood smear measures (Time 1). After collecting these measures, the RA will wait in the participant's room for 15 minutes. At 15-minutes post-intervention (Time 2), the RA will again collect PROs and a final peripheral blood smear measure.

After the final PRO and peripheral blood smear collection, the RA will ensure that the participant knows how to access the MARI recording and enter MDPRO measurements using the study iOS device or their own device, and that they have headphones and, if applicable, a dongle, in order to listen to the recording. The RA will instruct the participant to listen to the MARI intervention 3x/day and complete 3 MDPRO measurements each day until discharge. If the participant elects to use a study iOS device, it will be locked to the participant's tray table to prevent it from being lost or stolen during the participant's hospitalization.

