collecting any data, the RA , like on day one, will (1) check in with the treating physician and/or the clinical nurse; (2) ask the participant if their pain level will permit them to participate; and (3) ask the participant if they still want to participate in study procedures. If the participant responds affirmatively to continuing study procedures, the RA will document this in REDCap and then proceed with troubleshooting and data collection. The RA will record any barriers to MARI use and/or MDPRO collection (i.e., forgot, technical difficulties, off the floor for a procedure) as well as the participant's self-reported use of MARI in the last 24 hours. From Day 2 (i.e., the day after the live MARI intervention) until the participant is discharged from the hospital, participants using a study iOS device will receive three notifications per day (i.e., morning, afternoon, and evening) on the iOS device to complete MDPRO measures, and participants using their own device will receive three email or text invitations (per their preference) to complete the MDPRO measures. The participant's use of the MARI recording will be tracked using file utilization measures available within Box.com. No PHI will be entered into the Box.com folder. The RA will also track the participant's use of pain medications (recorded in the EHR or on the PCA). All data will be stored in REDCap.

On the day of the participant's discharge from the hospital, the RA will collect the study iOS device, if applicable. For those that don't already have the link on their own device, the RA will provide the participant with the MARI recording via email and a Box.com link to allow the participant to access the recording post-discharge. If desired, the RA will also provide the recording via a compact disk. Following discharge, the study coordinator will arrange a time for the participant to complete a semi-structured interview over Zoom. One to two weeks after the participant's discharge from the hospital, researchers will meet with the participant over a HIPAA-compliant commercial tele-health platform to complete a semi-structured interview (see Appendix for interview guide). If the participant is expected to be discharged over the weekend, the RA will provide the MARI recording resources on the Friday before the weekend in which the participant is to be discharged.

Blood sample procedures

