- 5. Pain medications administered (name, route, quantity, dose, time)
- 6. Surgery date
- 7. Surgery type
- 8. Significant surgical complications
- 9. Hospital floor
- 10. MARI intervention date
- 11. Music preferences
- 12. Imagery preferences
- 13. Discharge date

Patient reported outcomes pre-intervention (Time 0), post-intervention (Time 1) and 15-minutes post-intervention (Time 2), and three times per day (i.e., morning, afternoon, and evening) until the participant is discharged.

- 1. Pain (0-10)
- 2. Stress (0-10)
- 3. Anxiety (0-10)

Feasibility measures

- 1. Reasons for not completing MARI intervention (if applicable)
- 2. Reasons for not completing peripheral blood smear (if applicable)
- 3. Dates/times of accessing the MARI recording during participant's hospitalization
- 4. Self-reported use of MARI recording during participant's hospitalization
- 5. Reasons for not using MARI recording (if applicable)
- 6. Reasons for not entering MDPRO data (if applicable)
- 7. Reasons for study withdrawal (if applicable)

Semi-structured interview

- 1. Audio recording
- 2. Transcript

V4 03.22.2024 Page 10 of 16

| HRP- 503BIO | TEMPLATE: UH Biomedical Protocol | | |
|----------------|----------------------------------|----------------|---------|
| Approved: | 09/2021 | Prior Version: | 08/2019 |

Biological samples pre-intervention (Time 0), post-intervention (Time 1), 15-minutes post-intervention (Time 2).

1. Peripheral blood sample

Data Analysis Plan

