All attempts will be made to ensure participants' privacy. The referrals will come from the participant's medical team. The participant's name will only appear on the consent form and the linking log. The linking log that identifies the participant's study ID to identifiable data will be stored on a password-protected, encrypted computer or secure server. All data that is stored in REDCap will identify the participant by the number assigned to them at the beginning of the study. Informed consent will occur in a private clinical room or consult room out of the earshot of others to maintain privacy.

Only aggregate data will be presented or published and will be presented such that individuals cannot be identified. Only IRB-approved study personnel will have access to participant data. All study personnel will be required to be certified in the protection of human subjects throughout the study.

Identifiable information will not be reused or disclosed to any person or entity outside of University Hospitals other than those identified in the protocol, except as required by law, for authorized oversight of the research study, or as specifically approved for use in another study by the IRB.

Potential Benefit to Research Participants

V4 03.22.2024 Page 13 of 16

| HRP- 503BIO | TEMPLATE: UH Biomedical Protocol | | |
|----------------|----------------------------------|----------------|---------|
| Approved: | 09/2021 | Prior Version: | 08/2019 |

Although not guaranteed, there is the possibility that the MARI intervention may reduce pain, anxiety and stress after their surgery. Furthermore, future surgical patients may benefit from the knowledge gained from this study.

Withdrawal of Research Participants

The study doctor or the sponsor can withdraw participation of research participants at any time without their consent for the following reasons:

- If the patient is admitted to the ICU following surgery and remain admitted to the ICU on the day when study procedures would typically begin.
- If, after the first day participation, the participant's clinical condition deteriorates enough that they are transferred to the ICU.
- If it appears to be medically harmful to the subject;
- If the subject fails to follow directions for participating in the study;
- If it is discovered that the subject does not meet the study requirements;
- If the study is canceled; or

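### Weekday visits with a 24-hour recall leave most of each weekend's self-reported recording use unasked; separately, the 80% MDPRO criterion needs a stated denominator

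*Combined protocol and SAP*

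**What the plan says.** **Recording use.** Study Procedures has the RA see each participant daily on weekdays until discharge. At each visit the RA records self-reported use of the recording over the previous 24 hours. The same section tracks use through Box.com file logs. For an expected weekend discharge, it has the RA hand over the recording resources on the Friday before. The Feasibility measures list includes self-reported use during the hospitalization and, as a separate item, the dates and times at which the recording was accessed. The Data Analysis Plan will summarise "rates of enrollment, attrition, intervention participation, MARI recording use", among other rates. Interview procedures describes an interview one to two weeks after discharge about the participant's experience; its guide is in an appendix that is not reproduced.

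**MDPRO criterion.** Study Procedures states: "The RA will instruct the participant to listen to the MARI intervention 3x/day and complete 3 MDPRO measurements each day until discharge". The Data Analysis Plan counts it as failure if fewer than "80% of MDPRO measures over the duration of the participant's hospitalization" are completed, and plans to complete procedures among the "first 20 participants meeting full eligibility criteria". Withdrawal of Research Participants lists, as one of several discretionary grounds, "If the subject fails to follow directions for participating in the study"; transfer to intensive care after the first day is another. At each weekday visit participants are asked "if they still want to participate in study procedures". Reasons for missed MDPROs and for withdrawal are both recorded.

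**The concern.** The recall question and the visit schedule do not fit together. A 24-hour look-back covers the whole stay only if someone asks every day. With no weekend visits, Monday's answer reaches back to Sunday and stops. A measure described as covering the hospitalization then has a regular hole in it, on the days when no RA is there to help with problems. An analyst who totals the daily answers would understate use for anyone in hospital over a weekend, or would have to leave those days missing. At stake is the completeness of one descriptive measure.

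The second matter is an unwritten rule. The other three criteria carry counts (15/20, 15/20 and 45/60). The MDPRO criterion has a percentage but no count. It does not say whether prompts are pooled or averaged per participant, or what happens to prompts due after a participant is withdrawn. Because attrition is listed as its own rate beside PRO collection, an analyst could report a withdrawn participant only there. The figure compared with 80% is therefore not fixed for such participants.

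**Working it through.** **1. Recall gap.** Inputs: Monday-to-Friday visits and a 24-hour recall, both from Study Procedures. Visit times are not given.

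- Visits at the same hour: Friday to Monday is 72 h. Monday's recall covers 24 h, leaving 72 − 24 = 48 h unasked, or 48/72 = 67%.
- Assuming visits fall between 09:00 and 16:00: Friday 16:00 to Monday 09:00 is 65 h, leaving 65 − 24 = 41 h. Friday 09:00 to Monday 16:00 is 79 h, leaving 79 − 24 = 55 h.
- Weekend discharge: no later RA visit exists, so everything from Friday's visit to discharge is unasked. At most this is Friday 09:00 to the end of Sunday: 15 + 24 + 24 = 63 h.

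Between consecutive weekday visits at the same hour the gap is 24 − 24 = 0 h, so the problem is confined to weekends.

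**2. The plan's own figures.** Enrolment: 20/(1 − 0.33) = 29.85, rounded up to 30, which matches. 15/20 and 45/60 both equal the stated 75%. The 80% MDPRO criterion has no count to reproduce. The 33% allowance is defined as never meeting the pain criterion or choosing not to participate, so it does not say how someone withdrawn after starting is counted.

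**3. How much the MDPRO counting rule can matter.** The documents give no withdrawal rate, response rate or length of stay, so every input below is an assumption. Take 20 participants with 5 MDPRO days (15 prompts each). Two are withdrawn after 2 days, having answered 2 of 6 prompts each; the other 18 answer 85%.

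Completed: 18 × 15 × 0.85 + 2 × 2 = 233.5.

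| Rule | Calculation | Result |
|---|---|---|
| All prompts to discharge | 233.5/300 | 77.8% |
| Averaged per participant, to withdrawal | (18 × 0.85 + 2 × 2/6)/20 | 79.8% |
| Pooled, to withdrawal | 233.5/(270 + 12) | 82.8% |
| Withdrawn participants excluded | 0.85 | 85.0% |

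Changing only the number of MDPRO days:

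- 4 days: (18 × 12 × 0.85 + 4) = 187.6; 187.6/240 = 78.2% to discharge against 187.6/228 = 82.3% pooled to withdrawal.
- 10 days: (18 × 30 × 0.85 + 4) = 463; 463/600 = 77.2% against 463/552 = 83.9%.

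With only 1 withdrawn on the 5-day inputs, completed = 19 × 15 × 0.85 + 2 = 244.25. That is 244.25/300 = 81.4% to discharge and 244.25/291 = 83.9% pooled to withdrawal: the same verdict.

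A wider grid keeps 5 MDPRO days and one-third response before withdrawal. It varies the number withdrawn (1 to 4), the day of withdrawal (after day 1 to 4) and response in the others (85, 90 or 95%), giving 4 × 4 × 3 = 48 combinations. Opposite verdicts, summed over 85, 90 and 95%:

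- to discharge against pooled to withdrawal: 9 + 7 + 2 = 18;
- to discharge against exclusion: 12 + 7 + 2 = 21;
- pooled against averaged, both to withdrawal: 9 + 4 + 0 = 13.

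A change needs at least 2 withdrawn when the others answer 85%, 3 at 90% and 4 at 95%.

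**The case against.** On recall: Box.com records access at weekends, recording use has no pass/fail threshold, and the interview guide may already ask about weekend use. All of this stands, and it is why the point is of low severity. It does not make the self-report measure complete. The plan lists self-report and access logs as separate items, and the MDPRO prompts that continue over the weekend ask about pain, stress and anxiety, not recording use.

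On the MDPRO criterion: the phrase about the duration of the hospitalization, read with the first-20 cohort, already points to counting everyone to discharge. This largely stands; the lenient rules depart from the natural reading. A reader might go further and infer that poor responders would be withdrawn and so removed from their own denominator. The documents do not support that. The ground is one line in a general, discretionary list. The specific text on missed prompts has the RA troubleshoot barriers and record reasons, and nothing links missed prompts to withdrawal. Nor do the documents show that the rule would be chosen after the data are seen. The verdict changes above also rest on assumed inputs: counting to discharge and pooled counting to withdrawal agree in 48 − 18 = 30 of the 48 combinations, and one withdrawal never changes the result.

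What remains is that no passage gives the rule for participants withdrawn after starting, or says whether the figure is pooled or averaged. The second question arises even with no withdrawals, because lengths of stay can differ.

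**Conclusion.** The recall gap follows directly from two stated rules: 48 of 72 Friday-to-Monday hours with visits at the same hour, 41 to 55 hours under the assumed visit times, and everything after Friday's visit for weekend discharges. It leaves one descriptive feasibility measure incomplete and changes no threshold result. It is a cheap improvement of low severity.

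The MDPRO denominator is a clarification, not a demonstrated error. The choice can move the figure across 80% when 2 or more of 20 are withdrawn (77.8% against 82.8% in the example). That depends on assumed withdrawals, response and stay, and is possible rather than shown to be likely.

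**What to change.** **Recall.** Reword the RA item to ask about use since the previous RA visit, recorded by calendar day. For weekend discharges, ask about use after Friday's visit at the existing one-to-two-week interview, if the guide does not already do so. Cost: one REDCap item and at most one interview question, with somewhat longer recall on Mondays and at the interview.

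**MDPRO criterion.** State in the Data Analysis Plan that the denominator is every prompt due from Day 2 to discharge for all participants who received the live session. Prompts after any withdrawal, including transfer to intensive care, count as not completed in the main figure. Say whether the 80% is pooled or a per-participant average, and add a sensitivity figure that stops at withdrawal. Receipt of the live session is a better anchor than "Initiated study procedures", because that status is reached before the session, while Day 2 is defined as the day after it.

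Cost: a few sentences and possibly a less favourable percentage. The main figure also needs the discharge date of withdrawn participants. Discharge date is already a listed data item, but the plan should confirm that it may be collected after withdrawal. These changes concern counting only; the grounds for withdrawal are left as they are.
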